#### **Organ Function Assessments**

- 229 Hepatic dysfunction within 28 days prior to randomization:
  - direct bilirubin  $\geq$  1.5x the upper limit of normal (ULN)
  - aspartate aminotransferase (AST) or alanine aminotransferase (ALT)  $\geq$  2.5 x ULN
- 230 Left ventricular ejection fraction < 40% assessed by transthoracic echocardiogram (ECHO).
- 231 Absolute neutrophil count (ANC) <  $1 \times 10^9/L$  within 28 days prior to randomization. Screening ANC should be independent of growth factor support for  $\geq$  1 week.
- 232 Hemoglobin < 80 g/L within 28 days prior to randomization. Use of erythropoietic stimulating factors and red blood cell (RBC) transfusions per institutional guidelines is allowed; however, most recent RBC transfusion must not have been performed within 7 days prior to obtaining screening hemoglobin.
- 233 Platelet count <  $50 \times 10^9/L$  ( $\leq 30 \times 10^9/L$  if myeloma involvement in the bone marrow is > 50%) within 28 days prior to randomization. Subjects should not have received platelet transfusions for at least 1 week prior to obtaining the screening platelet count.
- 244 Calculated or measured creatinine clearance < 30 mL/min (calculation must be based on the Cockcroft and Gault formula) within 28 days prior to randomization.

#### **Other Exclusions**

- 235 Female subject is pregnant or breastfeeding or planning to become pregnant or breastfeed during treatment and for an additional 30 days after the last dose of all study drug(s). (Females of childbearing potential should only be included in

the study after a confirmed menstrual period and a negative highly sensitive urine or serum pregnancy test).

236 Female subjects of childbearing potential unwilling to use 2 methods of contraception (1 highly effective form of contraception and 1 additional effective contraceptive method) for at least 28 days before starting study drug(s), during treatment, during treatment interruptions, and for an additional 30 days after the last dose of all study drug(s). Refer to Section [12.5](#) for additional contraceptive information.

237 Female subjects of childbearing potential with a positive pregnancy test assessed at screening (by a highly sensitive serum pregnancy test 10 to 14 days prior to first dose of study drugs).

238 Male subjects with a female partner of childbearing potential who are unwilling to practice sexual abstinence (refrain from heterosexual intercourse) or use a condom with spermicide during treatment and for an additional 90 days after the last dose of all study drug(s), even if they have undergone a successful vasectomy. Refer to Section [12.5](#) for additional contraceptive information.

239 Male subjects with a pregnant partner who are unwilling to practice abstinence or use a condom with spermicide during treatment and for an additional 90 days after the last dose of all study drug(s).

240 Male subjects unwilling to abstain from donating blood, semen, or sperm during treatment and for an additional 90 days after the last dose of all study drug(s).

241 Females subjects unwilling to abstain from donating blood during treatment and for an additional 90 days after the last dose of all study drug(s).

242 Subject likely to not be available to complete all protocol-required study visits or procedures, and/or to comply with all required study assessments (including COA) to the best of the subject and investigator's knowledge.

243 History or evidence of any other clinically significant disorder, condition or disease (with the exception of those outlined above) that, in the opinion of the investigator or Amgen physician, if consulted, would pose a risk to subject safety or interfere with the study evaluation, procedures or completion.

### **6.3 Subject Enrollment**

Before subjects begin participation in any study-specific activities/procedures, Amgen requires a copy of the site's written institutional review board/independent ethics committee (IRB/IEC) approval of the protocol, informed consent form (ICF), and all other subject information and/or recruitment material, if applicable (see Section [12.3](#)).

The subject or the subject's legally acceptable representative must personally sign and date the IRB/IEC and Amgen approved informed consent before commencement of study-specific procedures.

A subject is considered enrolled when the investigator decides that the subject has met all eligibility criteria. The investigator is to document this decision and date in the subject's medical record and in/on the enrollment electronic case report form (eCRF).

Each subject who enters into the screening period for the study (defined as the point when the subject signs the informed consent) receives a unique subject identification number before any study-related activities/procedures are performed. The subject identification number will be assigned via Interactive Voice/Web Response System (IxRS). This number will be used to identify the subject throughout the clinical study and must be used on all study documentation related to that subject.

The subject identification number must remain constant throughout the entire clinical study; it must not be changed after initial assignment, including if a subject is rescreened. This number will not necessarily be the same as the randomization number assigned for the study.

#### **6.4 Screen Failures**

Screen failures are defined as subjects who consent to participate in the clinical study but are not subsequently enrolled in the study. A minimal set of screen failure information will be collected that includes demographics, screen failure details, eligibility criteria, and any serious adverse events. If a serious adverse event is observed from the time informed consent is signed up to the point of screen failure, then serious adverse events, medical history, and concomitant medications will also be collected.

Individuals who do not meet the criteria for participation in this study (screen failure) may be rescreened once. Refer to Section [9.1.1](#).

Subjects who experience a technical failure of central laboratory samples at screening (for example sample is lost or damaged in transit, or otherwise cannot be analyzed) will not be considered a screen failure. Central lab samples may be retested during screening in such cases, subject to the screening window not being exceeded.

### **7. Treatments**

Study treatment is defined as any investigational product(s), non-investigational product(s), placebo, combination products, or medical device(s) intended to be administered to a study subject according to the study protocol.

Note that in several countries, investigational product and non-investigational product are referred to as investigational medicinal product and non-investigational medicinal product, respectively.

The Investigational Product Instruction Manual (IPIM), a document external to this protocol, contains detailed information regarding the storage, preparation, destruction, and administration of each treatment shown below.

## **7.1 Treatment Procedures**

### **7.1.1 Investigational Product: Carfilzomib**

#### **7.1.1.1 Dosage Formulation**

Carfilzomib will be manufactured and packaged by Amgen and distributed using Amgen clinical study drug distribution procedures.

Carfilzomib is supplied as a sterile, lyophilized, white to off-white powder ready for reconstitution. It is supplied for single use in 50 mL Type 1 glass vials containing 60 mg of carfilzomib drug product with an elastomeric stopper and flip-off lid.

#### **7.1.1.2 Dosage, Administration, and Schedule**

Hematology and chemistry samples will be repeated within 3 days prior to cycle 1 day 1 and reviewed by the investigator before first dose.

Baseline laboratories for SPEP/UPEP/SIFE/UIFE/SFLC, will also be collected and checked by the investigator or treating physician before treatment is administered on cycle 1 day 1 if the screening laboratory assessments were not performed within 14 days of randomization.

#### Both arms:

Each subject's first dose of carfilzomib will be calculated based upon baseline body surface area (BSA) using the Mosteller formula. In subjects with  $BSA > 2.2 \text{ m}^2$ , the dose should be capped based on a BSA of  $2.2 \text{ m}^2$ . The dose for each subject should not be revised unless the subject has a change in body weight of  $> 20\%$  (gain or loss) in which case the BSA should be recalculated. Carfilzomib dose is to be recalculated using the updated BSA and applied until such time that any future weight change requires further BSA recalculation. The dose can also be modified in response to toxicity following the dose modification guideline tables using the most current BSA if this has been recalculated since the first cycle due to weight change.

Carfilzomib will be administered as an IV infusion. Mechanical infusion pumps are recommended, but gravity-dependent infusions are permitted if the infusion duration can be reliably maintained.

The planned dose (mg/m^2), quantity administered (mg), start date/time, stop date/time, reason for change in planned dose, reason for dose change/withheld, reason for dose delay, reason for dose interruption and package lot number of carfilzomib are to be recorded on each subject's eCRF.

**Arm 1 (once-weekly KRd 56 mg/m^2):**

Carfilzomib will be administered once-weekly IV as a 30 ± 5 minute infusion using an infusion pump on days 1, 8, and 15 of each 28-day cycle. The dose will be 20 mg/m^2 on day 1 of the first cycle and 56 mg/m^2 beginning with day 8 of cycle 1 and thereafter. All carfilzomib doses should be administered on the scheduled day ± 2 days, and the day 8 and 15 doses should have at least a 5-day treatment-free interval. Dose delays > 2 days are only permitted during the start of a new cycle.

**Arm 2 (twice-weekly KRd 27 mg/m^2):**

Carfilzomib will be administered twice-weekly IV as a 10 minute ± 5 minute infusion using an infusion pump on days 1, 2, 8, 9, 15, and 16 of each 28-day cycle. The dose will be 20 mg/m^2 on days 1 and 2 of the first cycle and 27 mg/m^2 beginning with day 8 of cycle 1 and thereafter.

Every effort should be made to maintain the days 1, 2, 8, 9, 15, and 16 of 28-day schedule. If this is not possible, then priority should be to maintain consecutive dosing days. For example, if day 1 of a new cycle is started 2 days later than originally scheduled, the entire cycle should shift by 2 days, such that the new days 1, 2, 8, 9, 15, and 16 of the next cycle are maintained. There must always be at least 5 days between the second dose of 1 week and the first dose of the following week (ie, between days 2 and 8, and days 9 and 15). Mid-cycle doses that are missed should not be made up unless these parameters are maintained.

**7.1.1.3        Intravenous Prehydration**

Subjects may receive IV prehydration (normal saline or other appropriate IV fluid) prior to each carfilzomib infusion during cycle 1. Investigators must consider IV prehydration in subjects at high-risk for tumor lysis or renal toxicity. All subjects must be monitored for fluid overload and hydration should be tailored to individual needs.

Thereafter, carfilzomib prehydration may only be administered if the subject's condition and/or risk factors require it. The total volume of prehydration and the indication will be recorded on the Concomitant Medications eCRF.

Carfilzomib infusion must occur at a facility capable of managing hypersensitivity reactions.

#### **7.1.1.4 Starting Dose in Hepatic Insufficiency**

For subjects with baseline chronic hepatic impairment (mild, moderate), reduce the starting and subsequent doses of carfilzomib by 25% (Brown et al, 2017):

- for once-weekly arm: 15 mg/m^2 day 1 of cycle 1 and 42 mg/m^2 day 8 of cycle 1 and thereafter;
- for twice-weekly arm: 15 mg/m^2 day 1 and 2 of cycle 1 and 20 mg/m^2 day 8 of cycle 1 and thereafter.

If hepatic function returns to normal, the dose may be re-escalated to 56 mg/m^2 (for once-weekly arm) and 27 mg/m^2 (for twice-weekly arm) after the first cycle. For dose modification due to subsequent changes in hepatic function, refer to Section [7.4.1.1.2](#).

Mild and moderate hepatic dysfunction is defined as:

- Mild: 1.0 x ULN < bilirubin ≤ 1.5 x ULN; or AST > ULN with bilirubin ≤ ULN
- Moderate: 1.5 x ULN < bilirubin < 3 x ULN with any AST

#### **7.1.2 Non-investigational Products**

##### **7.1.2.1 Dexamethasone: Dosage, Administration, and Schedule**

Dexamethasone, a non-Amgen non-investigational product, will also be used in this study. Dexamethasone should be taken weekly orally or by IV infusion at a dose of 40 mg. When dexamethasone is administered on the same day as carfilzomib, it should be started and completed within 4 hours of the start of carfilzomib infusion. A 30 minute interval between the end of the dexamethasone infusion and the start of the carfilzomib infusion is recommended. All doses should be administered on the scheduled days ± 2 days.

The planned dose, quantity administered, start date/time, stop date/time, route, reason for dose change/withheld, reason for dose delay, reason for dose interruption are to be recorded on each subject's eCRF.

##### **7.1.2.2 Lenalidomide**

###### **7.1.2.2.1 Prescribing Requirements**

Lenalidomide, a non-Amgen non-investigational product, will also be used in this study.

Within the United States, lenalidomide should be administered in accordance with the REVLIMID REMS® program of Celgene Corporation (<http://www.revlimidrems.com/>) All physicians who prescribe lenalidomide for research subjects enrolled into this study, and

---

all research subjects enrolled on this study, must be registered in and comply with all requirements of the REVLIMID REMS® program.

Females of childbearing potential (FCBP) must agree to monitoring for pregnancy. In addition, males and FCBP are subject to certain restrictions as detailed in Section 12.5 while receiving lenalidomide.

Outside the United States, all investigators and subjects must adhere to the requirements of the lenalidomide restricted distribution program in effect in their local country.

#### **7.1.2.2.2 Dosage, Administration, and Schedule**

In subjects with normal renal function, lenalidomide will be taken once-daily orally on days 1 to 21 of each cycle at a dose of 25 mg. In subjects with renal impairment (mild to moderate or severe), please refer to the regional product label. Lenalidomide should be taken at home by the subject at about the same time each day. Lenalidomide capsules should be swallowed whole with water. The capsules should not be opened, broken, or chewed. If a planned dose is missed, it should be taken as soon as possible within the same calendar day and with a return to the regular schedule the following day. If a planned dose is missed for more than a calendar day, subjects should not make up doses, but should resume the dosing regimen as per schedule. Dose modifications are permitted in response to toxicity following the dose modification guideline tables.

The planned dose, quantity administered, start date, and reason for dose change are to be recorded on each subject's eCRF.

#### **7.1.3 Medical Devices**

No investigational medical devices will be used.

Other non-investigational medical devices may be used in the conduct of this study as part of standard care.

Non-investigational medical devices (eg, syringes, sterile needles), that are commercially available are not usually provided or reimbursed by Amgen (except, for example, if required by local regulation). The investigator will be responsible for obtaining supplies of these devices.

#### **7.1.4 Other Protocol-required Therapies**

All other protocol-required therapies including, antiviral prophylaxis, thromboprophylaxis, tumor lysis prophylaxis, proton pump inhibitor, bisphosphonate therapy, and prophylaxis

for *Pneumocystis jirovenci* pneumonia, that are commercially available are not provided or reimbursed by Amgen (except if required by local regulation). The investigator will be responsible for obtaining supplies of these protocol-required therapies.

#### **7.1.4.1 Antiviral Prophylaxis**

An antiviral is a required concomitant medication for the duration of treatment with carfilzomib. Acyclovir (eg, 400 mg orally 3 times a day, or 800 mg orally 2 times a day or per institutional standards), famcyclovir (eg, 125 mg orally given 3 days, twice a day or per institutional standards), or valacyclovir (eg, 500 mg orally, twice a day or per institutional standards), dose adjustments for renal function where appropriate, initiated within 1 week of the first dose of carfilzomib and should continue for the duration of treatment with carfilzomib.

#### **7.1.4.2 Prophylaxis for Hepatitis B Reactivation**

Hepatitis B virus (HBV) reactivation prophylaxis should be considered for patients at risk (ie, patients tested positive on serology or had a prior history of HBV infection) as per institutional standards.

#### **7.1.4.3 Thromboprophylaxis**

It is strongly recommended that all subjects receive an anticoagulant (eg, low molecular weight heparin, direct oral anti-coagulant, warfarin, enteric-coated aspirin at standard prophylactic dose or other anticoagulant or antiplatelet medication). Additional or secondary thromboprophylaxis medication is strongly recommended in subjects with elevated risk of thrombosis, based on an individual benefit/risk assessment (Li et al, 2017).

#### **7.1.4.4 Tumor Lysis Syndrome Prophylaxis**

An approved uric acid-lowering agent (eg, allopurinol) in subjects at high-risk for tumor lysis syndrome (TLS) due to high tumor burden may be prescribed at the investigator's discretion, according to the package insert.

Subjects should be well hydrated to reduce the risk of TLS and decline in renal function; refer to the current Carfilzomib IB for safety guidance regarding TLS.

#### **7.1.4.5 Proton-pump Inhibitor**

Proton-pump inhibitor (omeprazole or equivalent) is required while on dexamethasone.

#### **7.1.4.6 Bisphosphonate or Monoclonal Antibody Therapy**

Concomitant therapy should be administered to all subjects with evidence of lytic destruction of bone or with osteopenia (Gralow et al; 2013; Terpos et al, 2013) unless

contraindicated. Commercially available therapies are preferred when available and should be used for subjects with osteolytic or osteopenic myelomatous bone disease according to the manufacturer's recommendations, as described in the prescribing information.

Subjects who are using bisphosphonate or monoclonal antibody therapy when they enter the study should continue the same treatment. Subjects with evidence of lytic destruction of bone or with osteopenia who are not using a bisphosphonate or monoclonal antibody therapy at the time of randomization should start therapy as soon as possible during cycle 1 or 2 of treatment. Investigators should not start bisphosphonate or monoclonal antibody therapy during the study, unless it has been agreed with the sponsor that there is no sign of disease progression.

#### **7.1.4.7 Prophylaxis for *Pneumocystis Jirovenci***

*Pneumocystis jirovenci* pneumonia prophylaxis should be considered, as per institutional guidelines while on dexamethasone.

#### **7.1.5 Other Treatment Procedures**

No other treatment procedures are required.

#### **7.1.6 Product Complaints**

A product complaint is any written, electronic, or oral communication that alleges deficiencies related to the identity, quality, durability, reliability, safety, effectiveness, or performance of a drug, combination product, or device after it is released for distribution to market or clinic by either (1) Amgen or (2) distributors or partners for whom Amgen manufactures the material. This includes all components distributed with the drug, such as packaging drug containers, delivery systems, labeling, and inserts.

This includes any investigational products provisioned and/or repackaged/modified by Amgen: carfilzomib.

Any product complaint(s) associated with an investigational product(s) or non-investigational products(s) supplied by Amgen are to be reported according to the instructions provided in the IPIM.

#### **7.1.7 Excluded Treatments, Medical Devices, and/or Procedures During Study Period**

##### **7.1.7.1 Anticancer Therapeutic or Radiation**

Concurrent therapy with a marketed or investigational anticancer therapeutic or radiation to large marrow reserves for either a palliative or therapeutic intent is excluded.

#### **7.1.7.2        Corticosteroids**

Long-term corticosteroids for nonmalignant conditions (eg, asthma, inflammatory bowel disease) equivalent to a dexamethasone dose > 4.0 mg/day or prednisone > 20 mg/day are not permitted. Corticosteroids given short-term (up to 2 weeks) for non-malignant conditions are permitted provided that the cumulative dose is less than 40 mg per week dexamethasone equivalent. Medical monitor should be contacted if short-term corticosteroid use is required > 2 weeks or at cumulative dose of more than 40 mg dexamethasone equivalent.

#### **7.1.7.3        Plasmapheresis**

Plasmapheresis is not permitted at any time while the subject is receiving study treatment. For subjects requiring plasmapheresis while on study treatment, every attempt should be made to document disease status by IMWG criteria first. Study treatment must be discontinued.

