**Table 7-1. Dose Decremnts for Carfilzomib**

Nominal Dose (mg/m  )	Reduced Carfilzomib Doses (mg/m  )			
	Dose -1	Dose -2	Dose -3	Dose -4
20 a, b	15	11	Discontinue	-
27	20	15	11	Discontinue
56	45	36	27	20

a If dose reduction of carfilzomib is required on cycle 1 day 1 or cycle 1 day 2, the investigator should contact the medical monitor to discuss the situation before any additional doses of carfilzomib are administered.

b For subjects with baseline chronic hepatic impairment (mild, moderate), reduce the starting and subsequent doses of carfilzomib by 25% (ie, for once-weekly arm: 15 mg/m^2 day 1 of cycle 1 and 42 mg/m^2 day 8 of cycle 1 and thereafter; for twice-weekly arm: 15 mg/m^2 day 1 and 2 of cycle 1 and 20 mg/m^2 day 8 of cycle 1 and thereafter).

The subject will be considered on protocol treatment while receiving carfilzomib or lenalidomide.

If day 1 of a cycle is delayed, all subsequent doses within the cycle and also day 1 of subsequent cycles should be adjusted accordingly to maintain the 28-day cycle duration. However, if a within-cycle dose is delayed, then the dates of the subsequent within-cycle doses should not be adjusted. For within-cycle doses, if administration does not

commence within the allowable window of the scheduled administration date, then the dose will be considered a missed dose and this missed dose will not be made up. Administration may resume at the next planned dosing date.

If a subject requires interruption of carfilzomib for more than 6 consecutive weeks due to unresolved toxicities, the subject must be discontinued permanently from study treatment.

If a subject requires interruption of carfilzomib for more than 6 weeks for reasons other than toxicity, medical monitor approval is required prior to resuming treatment. The reason for dose change of carfilzomib is to be recorded on each subject's eCRF.

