**Table 7-3. Dose Modification Guidelines for Nonhematologic Toxicities**

Symptom/Sign/Investigation	Recommended Action
Thrombotic microangiopathy: Fever, microangiopathic hemolytic anemia, renal failure, thrombocytopenia, neurological manifestations	If the diagnosis is suspected, hold carfilzomib and manage per standard of care including plasma exchange as clinically appropriate. If TMA is confirmed, permanently discontinue carfilzomib. If the diagnosis is excluded, carfilzomib can be restarted
Venous thrombosis ( $\geq$ grade 3)	Hold carfilzomib and adjust anticoagulation regimen; resume at full dose once anticoagulation has been optimized per treating investigator's discretion.
Any other drug-related nonhematologic toxicity $\geq$ grade 3 b	For carfilzomib attribution, hold dose. Resume at 1 dose decrement when toxicity has resolved to grade 1 or less or to baseline grade.

Page 3 of 3

ALT = alanine aminotransferase; ANC = absolute neutrophil count; ARDS = acute respiratory distress syndrome; AST = aspartate aminotransferase; CrCl = creatinine clearance; DBP = diastolic blood pressure; LDH = lactate dehydrogenase; MRI = magnetic resonance imaging; NCI-CTCAE = National Cancer Institute-Common Terminology Criteria for Adverse Events; PRES = Posterior Reversible Encephalopathy Syndrome; SBP = systolic blood pressure; TMA = thrombotic microangiopathy; ULN = upper limit of normal.

a For a rapid fall from baseline in CrCl or an absolute fall of  $\geq$  60 mL/min, contact the medical monitor.

b In the event of a possible drug-related nonhematologic toxicity, the investigator should, to the best of his/her ability, assess its relationship to lenalidomide (R), carfilzomib (K), dexamethasone (d), or the combination of KRd to the extent possible. If both carfilzomib and lenalidomide are considered likely to be involved, then recommended actions for both should be instituted.

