- Immunoglobulin (Ig) G multiple myeloma: serum monoclonal paraprotein (M-protein) level  $\geq 1.0$  g/dL,
- IgA, IgD, IgE multiple myeloma: serum M-protein level  $\geq 0.5$  g/dL,
- urine M-protein  $\geq 200$  mg/24 hours,
- in subjects without measurable serum or urine M-protein, serum-free light chain (SFLC)  $\geq 100$  mg/L (involved light chain) and an abnormal serum kappa lambda ratio

Determination of PD while on study requires 2 consecutive assessments (to confirm response or PD, 2 discrete samples are required; samples may be drawn on the same day) before classification of PD and/or the institution of new therapy. Confirmative samples for PD after new therapy can be used. Serum M-component increases of  $\geq 1$  g/dL from nadir are sufficient to define progression if nadir M-component is  $\geq 5$  g/dL.

Plasmacytomas: A plasmacytoma is considered measurable if the longest diameter is at least 1 cm and the product of the cross diameters is at least 1 cm^2. Progression is defined as appearance of a new lesion(s),  $\geq 50\%$  increase from nadir of the sum of the products of the maximal perpendicular diameter (SPD) of the measurable lesion as measured serially, or a  $\geq 50\%$  increase in the longest diameter of a previous lesion  $> 1$  cm short axis;  $\geq 50\%$  increase in plasma cells if this is the only measure of disease.

---

For defining nadir, in the case where a value is felt to be a spurious result per physician/Independent Review Committee (IRC) discretion (eg, a possible laboratory error), that value will not be considered when determining the lowest value.

Sources: Kumar et al, 2016; Rajkumar et al, 2011; Durie et al, 2006.

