4.2 Subgroups

The ORR, **PFS** and **OS** will be estimated for the following selected subgroups defined by the baseline data reported on CRF or from the central lab, as appropriate. When there is not a sufficient number of subjects in the subgroup, i.e., less than 5% of the whole population, relevant subgroups may be combined.

- original ISS stage at baseline (stage 1 or 2 vs stage 3)
- prior lenalidomide treatment (yes vs no)
- prior PI treatment (yes vs no)
- prior anti-CD38 exposure (yes vs no)
- prior bortezomib treatment (yes vs no)
- age (years) (<65, ≥65; 18 - <65, 65 - <75, ≥75)
- region (Europe vs Non-Europe)
- baseline creatinine clearance (CrCl, mL/min) (<50, ≥50)
- number of prior therapies (1 vs >1; 1 vs 2 vs >2)
- cytogenetic risk measured by FISH (high-risk (t(4;14), t(14;16), deletion 17p) vs standard risk)
- bortezomib refractory status (yes vs no)
- lenalidomide refractory status (yes vs no)
- prior transplant (yes vs no)

5. Definitions

Baseline

The baseline value is the latest value measured on/before day 1 of the first dose of any protocol-specified therapy. If a subject doesn't receive any protocol-specified therapy, then the latest value prior to or on randomization date will be used.

For bone lesion and plasmacytoma assessment, the baseline is defined as the most recent assessment within 45 days (bone lesion) or 28 days (plasmacytoma) prior to or on the randomization date, or up to 7 days (inclusive) after initiation of the study treatment if the patient has been dosed.

Best overall response by investigator assessment

Best overall response for a subject by investigator assessment is the best post baseline confirmed response by the analysis trigger date based on the responses by visit collected on myeloma response assessment CRF. The response assessments done after confirmed disease progression or initiation of new anti-myeloma therapy will be excluded from the analysis of primary endpoint.

Best overall response by IRC assessment

Best overall response for a subject by IRC as collected on IRC Evaluation CRF. Details of the IRC will be described in the IRC charter.

Cytogenetic Risk group as determined by Fluorescent in Situ Hybridization (FISH)

Cytogenetic risk group is defined based on the central laboratory FISH analytes t(4;14), t(14;16) and deletion 17p regardless of any other FISH analyte test results.

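### Section 7.1.7.3 bans plasmapheresis and requires study treatment to stop, while the TMA row of Table 7-3 holds only carfilzomib, allows plasma exchange and permits restart; the two must be reconciled

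*Protocol*

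**What the plan says.** Protocol Section 7.1.7.3, in the list of excluded treatments and procedures, says: "Plasmapheresis is not permitted at any time while the subject is receiving study treatment". For a subject who needs it, sites are asked to try to record IMWG disease status beforehand, and then: "Study treatment must be discontinued".

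The TMA row of Protocol Table 7-3 says: "If the diagnosis is suspected, hold carfilzomib and manage per standard of care including plasma exchange as clinically appropriate". If TMA is confirmed, carfilzomib is stopped for good. Otherwise: "If the diagnosis is excluded, carfilzomib can be restarted".

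The text below Table 7-1 (Section 7.4.1.1) adds: "The subject will be considered on protocol treatment while receiving carfilzomib or lenalidomide". Section 7 defines study treatment to include non-investigational products, which Section 7.1.2 lists as dexamethasone and lenalidomide.

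On the endpoints, the SAP Section 5 definition of best overall response by investigator says: "The response assessments done after confirmed disease progression or initiation of new anti-myeloma therapy will be excluded from the analysis of primary endpoint". The next definition takes best overall response by IRC from the IRC form and refers to the IRC charter for details. SAP Table 5-1 gives the PFS censoring rules.

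**The concern.** The two protocol passages give different instructions for the same event. A site following Section 7.1.7.3 stops study treatment and treats the exchange as a prohibited procedure. A site following Table 7-3 holds one drug, treats the exchange as accepted management, and may resume carfilzomib. Subjects with the same event could therefore have different exposure, different reasons for discontinuation and different deviation records, depending on which page the site consulted.

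There is a smaller analysis question. By asking for IMWG status before plasmapheresis, Section 7.1.7.3 implies that readings taken afterwards may be hard to interpret. Overall response is the primary endpoint and rests largely on M-protein. One would expect the analysis rules to say what happens to assessments made after an exchange.

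**Working it through.** The plan gives no figure on this point, so the check sets the passages side by side.

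**Step 1: the two clinical rules applied to one subject.** Take a subject on all three drugs with suspected TMA who is given plasma exchange.

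| Situation | Section 7.1.7.3 | Table 7-3, TMA row |
|---|---|---|
| Exchange while on treatment | Not permitted | Accepted where clinically appropriate |
| TMA suspected, exchange given | Study treatment discontinued | Carfilzomib held; row silent on the other two drugs |
| TMA then excluded | No provision for resuming | Carfilzomib may restart |
| TMA then confirmed | Study treatment discontinued | Carfilzomib permanently stopped; row silent on the other two drugs |

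The columns differ in every line. Neither passage cross-refers to the other or states an exception.

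**Step 2: can the passages be read together?**
- *A carfilzomib hold takes the subject off study treatment, so the ban does not apply.* This fails. Study treatment covers lenalidomide and dexamethasone, and Section 7.4.1.1 keeps a subject on protocol treatment while lenalidomide continues.
- *Plasmapheresis and plasma exchange are different procedures.* The documents define neither term and draw no distinction.
- *Discontinued means paused.* Section 7.4.1.1 lists discontinuation separately from temporary delay, and Section 7.1.7.3 describes no resumption.

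**Step 3: what the analysis rules say about assessments after an exchange.**
- Protocol Section 9.2.2 continues disease assessments every 28 ± 7 days through dose delays and treatment discontinuation. Section 9.1.4 continues them after discontinuation until PD, new antimyeloma treatment, 12 months from randomization or another listed end.
- The investigator best-response definition removes assessments after confirmed PD or new anti-myeloma therapy. Plasma exchange is not named.
- SAP Table 5-1 has seven situations, none of which is plasma exchange.
- Protocol Section 10.2.1.3 excludes users of prohibited medications from the per-protocol population but does not name procedures. The treatment non-compliance list in SAP Section 6.3 (IPD criteria 500, 502, 801, 802, 803) has no item for prohibited therapies or procedures. The per-protocol analysis would not by these rules remove such subjects.
- SAP Sections 9.1 and 9.5.1 base the primary ORR analysis on IRC assessment. The IRC charter is not among the documents.

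The visible rules are therefore silent. Silence in the SAP does not show what the IRC does.

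**Step 4: direction of any effect.** PR in Appendix 11 needs a serum M-protein fall of at least 50% together with the urine criterion. On confirmation the appendix says: "to confirm response or PD, 2 discrete samples are required; samples may be drawn on the same day". A temporary fall could thus help a subject meet PR. PD is a 25% rise from the lowest confirmed value. A temporary fall could delay biochemical PD by keeping M-protein low, or bring it forward by setting a lower reference from which it rebounds. Appendix 11 lets the physician or IRC disregard a spurious value, but only when setting the nadir, and at their discretion.

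**The case against.** The strongest reply is that the clash over restart is narrow: it arises only if exchange is given on suspicion and TMA is then excluded. That is right about restart, but it does not remove the conflict. The ban itself, and the scope of what must stop, also differ when TMA is confirmed, because Table 7-3 then stops carfilzomib only.

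On the endpoints the other side has more. A reader might infer that assessments after exchange count in the primary analysis and that the resulting M-protein fall will be scored as response. The documents do not support that. The quoted exclusion sits in the investigator definition, the primary analysis uses IRC response, and the charter may contain a rule. The endpoint is best response, so an exchange after a genuine response changes nothing; Protocol Section 3.1.1 reports a mean time to response of 1.6 months on KRd in ASPIRE. PR also needs the urine criterion and, where a plasmacytoma was present at baseline, its shrinkage.

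A reader might also infer a material threat to the non-inferiority result, since Protocol Section 10.3.1.3 puts success at 84.3% against 86.6%: 0.843 × 230 = 193.9 and 0.866 × 230 = 199.2, about 5 responders apart. That comparison says nothing about plasma exchange. The documents give no frequency for it, and an affected assessment is not a misclassified responder.

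A third inference would be that focal radiotherapy opens the same gap, because Section 7.1.7.1 excludes only radiation to large marrow reserves. Appendix 11 requires plasmacytoma shrinkage in addition to the M-protein or light-chain criteria, so shrinkage of an irradiated lesion cannot by itself produce a PR.

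**Conclusion.** The contradiction between Section 7.1.7.3 and the TMA row of Table 7-3 is established from the current text. Sites cannot follow both, and whether an exchange for suspected TMA is a deviation depends on which passage is applied. This conclusion assumes only that plasmapheresis and plasma exchange mean the same procedure, which nothing in the documents contradicts.

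The endpoint part is a gap in what the SAP states. It is not a demonstrated bias. The number of subjects affected is unknown and probably small, which is an assumption because no rate is given. No overall effect on ORR can be computed, and the direction of any effect on PFS is uncertain. It warrants a question about the IRC charter and a sensitivity analysis, with no change to the primary analysis.

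**What to change.** 1. Reconcile Section 7.1.7.3 with the TMA row of Table 7-3 and cross-refer them. The agreed text should state which study drugs the instruction covers and whether exchange for suspected TMA is recorded as a deviation. The choice of clinical rule belongs to the sponsor and its clinical advisers.
2. Confirm how the IRC charter handles M-protein assessments after plasma exchange, and state that handling in SAP Section 5.
3. Add a sensitivity analysis of ORR and PFS that uses only disease assessments before the first recorded plasma exchange, specifying in advance how later deaths are treated. Leave the primary censoring rules in Table 5-1 unchanged: the SAP says they follow ASPIRE, the reference for the synthesis test, and censoring at an exchange that may be driven by toxicity would depart from that match.

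The cost is one protocol clarification, a few lines in the SAP and a little extra analysis. One limit remains. Protocol Section 7.8.2 collects concomitant therapies only to 30 days after the last dose, whereas disease assessments can run to 12 months after randomization. Later exchanges may therefore not be captured.
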